## STUDY DESIGN

**Overview:** This study will rigorously test the Community-Based Mentoring (CBM) program of Big Brothers Big Sisters of America (BBBSA) through a randomized control trial conducted in 16 BBBSA affiliates with approximately 1,356 youth, age 10 or older at enrollment. The measurement strategy will be multi-source/multi-informant. Youth will be the primary informant for most outcomes while parents will be the sole reporter on more “objective” outcomes they would be aware of (e.g., suspensions) and a second reporter on outcomes benefiting from triangulation (e.g., delinquent behavior, aggressive behavior, academic success). Youth and parent surveys will be administered cost-efficiently at baseline and both 18 months and 4 years later; official records of delinquency/crime will be collected twice for all participants: once at the end of the 18-month data collection period, to assess arrests for each youth through 18 months post-baseline, and again 2.5 years later to assess arrests for each youth through 4 years post-baseline; see **Appendix A** for timeline, which is current for all amendments to the original study plan that are referenced in this document). Based on the current age distribution of youth at enrollment into the CBM program, by this latter time point roughly two-thirds of the sample will be at least 16 years old, which is the peak age of onset for serious violence in the U.S. (U.S. Office of the Surgeon General, 2001).

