**Study Measures:** Official delinquency and crime records will be collected from relevant juvenile and criminal (i.e., adult) court authorities, relying on statewide data repositories when available for efficiency and maximum jurisdictional coverage. Records of all offenses committed by the youth that have been referred to juvenile or criminal court (both crimes and status offenses, such as truancy) up to the point of data collection will be collected, with data collected on two occasions: after 18-month survey data collection has ended and 2.5 years later (so as to ensure availability of arrest data for a period of four years from the time of each youth's date of study enrollment). The format of this information will vary given differences in court information systems. The researchers will work with NCJJ staff to translate data into a common format. Data elements that are expected to be available consistently across jurisdiction include: a) date of arrest; b) date and type of offense; and c) date and nature of adjudication and type of sentence (if any). This approach is not without limitations, as it will exclude offenses that are handled solely by law enforcement (e.g., decline to arrest or arrest but with diversion); however, consultation with NCJJ suggests it would be very challenging to collect adequate data on such incidents due to the multiple law enforcement agencies involved in any given affiliate's catchment area as well as a lack of consistent recording of data across agencies. Questions will be included on the youth and parent surveys, however, that ask about all arrests and police contacts, adapted from the Add Health Study (Bearman et al., 1997). In some instances, it may be possible to obtain official delinquency and crime records only in de-identified form (i.e., without the ability of researchers to identify the youth to whom the data apply); in these cases, at a minimum, the data obtained will include a dichotomous indicator of arrest history as of the date of study enrollment, a dichotomous indicator of whether or not the participant had an arrest during the relevant time window (e.g., 18 months from date of baseline), and treatment/control status. To the extent that is feasible (i.e., does not allow deductive identification of participants) and is allowed by data sharing entities, additional data elements (e.g., age, gender, self-reported delinquency at study baseline) that represent planned and/or potential control variables in study analyses also will be included in the shared dataset to provide access to these variables with the returned deidentified dataset.

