**Primary H1:** Program participation will decrease the likelihood that youth will have a court-related arrest for any of the following types of offenses during the 18 months after study enrollment and during the entire 4 year period of follow-up after study enrollment: person offense, property offense, drug law violation, public order offense, or status offense (i.e., binary variables indicating whether the youth has had an arrest for any of the indicated types of offenses);

**Primary H2:** Program participation will decrease the likelihood of youths’ involvement in both property-related and violence-related delinquent behavior during the preceding 18 months at the 18-month survey assessment and during the preceding 2.5 years at the 4-year survey assessment (i.e., binary variables indicating involvement or not in each type of delinquent behavior as described previously in this plan);

**Primary H3:** Program participation will decrease the likelihood of youths’ involvement in any substance use (i.e., any report of alcohol use to point of drunkenness, tobacco/vaping, or illicit drug use) during the preceding 18 months at the 18-month survey assessment and recurring substance use (i.e., alcohol use to the point of drunkenness “at least once every week or two”, illicit drug use “at least once a month”, or tobacco/vaping “at least once or twice a week”) during the preceding six months at the 4-year survey assessment (i.e., binary variables indicating whether or not the youth reports substance use as defined above);

**Secondary H1:** Program participation will *decrease* risk factors for delinquent/criminal behavior (i.e., school misbehavior, truancy, aggressive behavior, association with deviant peers, depressive symptoms, averaging youth and parent reports after standardization when both are available for continuous measures or creating a dichotomous measure of parent or youth endorsement vs. endorsement by neither in the case of truancy) as assessed 18 months after enrollment and again 4 years after enrollment;

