Generalized linear and nonlinear mixed-effects models (Bryk & Raudenbush, 1992; Fitzmaurice et al., 2004) will be used to test study hypotheses as these models can account for dependence among outcomes due to nesting of youth within both sites and families (i.e., siblings) as well as varying distributions of outcomes (e.g., binary, ordinal, continuous). Intercepts for sites and families within sites will be modeled as random and impact coefficients will be modeled as fixed. Covariates for tests of primary hypotheses will include youth demographics (i.e., age, gender, race/ethnicity, family structure, family income), baseline values of each primary outcome (i.e., history of court-related arrest pre-dating study enrollment, de-

linquent behavior, and substance use [presence or absence of substance use at baseline since recurring substance use was not assessed at baseline in the form it is being assessed at 4-year follow-up]), youth and parent reports of the youth's history, if any, of contacts with law enforcement not leading to arrest, and any other study measure of a potential contextual, behavioral, or attitudinal influence on criminal/delinquent behavior for which there is evidence of a non-negligible association with treatment/control group status (effect size of .05 or greater, per WWC standards, 2011). The same covariates will be used for tests of secondary hypotheses, with the addition of scores on the same measure or, where not available (as will be the case for some of the outcomes assessed at the 4-year follow-up for Secondary H3), the most closely related measure at baseline (i.e., strongest association), excluding those to be included as covariates in all analyses. Note that the analytic approach used will thus be ANCOVA (i.e., control for baseline scores on the outcome measures treated as a covariate) rather than a difference-in-differences approach (e.g., repeated-measures ANOVA).

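### Primary H1 dates its event by the arrest, so an arrest after enrollment for an offense committed before enrollment counts as an outcome; the cost is modest dilution and lost power, not bias

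*Combined protocol and SAP*

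**What the plan says.** Under Analysis, Primary H1 asks whether "youth will have a court-related arrest for any of the following types of offenses during the 18 months after study enrollment", with a parallel outcome over the full 4 years. It is coded as "binary variables indicating whether the youth has had an arrest for any of the indicated types of offenses". The other descriptions of this outcome also attach the window to the arrest:

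- The Overview says the first records pull is "to assess arrests for each youth through 18 months post-baseline".
- Study Measures says the second pull is timed "so as to ensure availability of arrest data for a period of four years from the time of each youth's date of study enrollment".
- Where records come back only in de-identified form, the guaranteed outcome field is "a dichotomous indicator of whether or not the participant had an arrest during the relevant time window".

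The matching baseline covariate is "history of court-related arrest pre-dating study enrollment".

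Study Measures also states: "Data elements that are expected to be available consistently across jurisdiction include: a) date of arrest; b) date and type of offense". So the offense date is expected in the data. No section uses it to define an H1 event, and none of the eight listed sensitivity analyses varies the date rule.

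**The concern.** Consider a youth who offends the month before enrollment and is first arrested the month after. H1 counts this as an event in the follow-up period, while the baseline arrest covariate records no history. The program had no chance to prevent that offense. Events of this kind arise at the same expected rate in both arms and pull the risk ratio toward 1. The plan already concedes reduced power and few events for the arrest outcome.

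The survey outcome in Primary H2 is handled differently: its 18-month recall frame was set to cover behavior since baseline. H1 and H2 therefore treat pre-baseline behavior differently, and the plan gives no reason.

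Timing matters where records are de-identified. If only a yes/no indicator is returned, the researchers cannot apply an offense-date rule afterward. It has to be in the data request.

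**Working it through.** **1. Reference power figure.** The plan states no lag and no share of arrests for earlier offenses, so there is no figure of its own to reproduce on this point. Its power statement serves as a reference case.

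Inputs from the power paragraph under Analysis: about 1,350 youth, 20% attrition, and 80% power for 10% vs 5.2%. The 3:1 allocation comes from the randomization section. This gives 1,350 × 0.8 = 1,080, or 270 control and 810 treatment. Two-sided .05 is my assumption, as the plan does not state it for these figures.

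Power = Φ[(|p1 − p2| − 1.96·s0)/s1], with s0 the pooled and s1 the unpooled standard error.

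- Pooled rate: (27 + 42.12)/1,080 = 0.064
- s0 = √[0.064 × 0.936 × (1/270 + 1/810)] = 0.0172
- s1 = √[0.10 × 0.90/270 + 0.052 × 0.948/810] = 0.0199
- Power = Φ(0.72) = 0.764, against the stated 0.80

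That shortfall is a separate matter. Here 0.764 is only the starting value.

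**2. Share of arrests in the window that are for earlier offenses.** Assume a constant offense rate and an exponential offense-to-arrest lag L with mean m months. For a window of W months, share = E[min(L, W)]/W = m(1 − e^(−W/m))/W.

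| Mean lag (assumed) | W = 18 | W = 48 |
|---|---|---|
| 0.5 month | 2.8% | 1.0% |
| 1 month | 5.6% | 2.1% |
| 2 months | 11.1% | 4.2% |
| 3 months | 16.6% | 6.2% |

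If offending instead grows exponentially, doubling over 18 months (assumed), the 1-month-lag share falls from 5.6% to about 3.9%. If it quadruples over 4 years (assumed), the share falls from 2.1% to about 1.0%. If offending peaks just before enrollment, the shares rise.

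**3. Effect on the comparison.** Let f be the share of control-arm events that are for earlier offenses and so unaffected by assignment. Apply the plan's risk ratio, 5.2/10 = 0.52, to the rest. At f = 10%, the treatment rate by arrest date is 1.0% + 9.0% × 0.52 = 5.68%. By offense date the comparison is 9.0% vs 4.68%. The risk difference is 4.32 points either way; the offense-date version has the smaller variance.

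| f | By arrest date | Risk ratio | Power | By offense date | Power |
|---|---|---|---|---|---|
| 0 | 10% vs 5.20% | 0.520 | 0.764 | 10% vs 5.20% | 0.764 |
| 4% | 10% vs 5.39% | 0.539 | 0.727 | 9.6% vs 4.99% | 0.748 |
| 5% | 10% vs 5.44% | 0.544 | 0.717 | 9.5% vs 4.94% | 0.743 |
| 10% | 10% vs 5.68% | 0.568 | 0.667 | 9.0% vs 4.68% | 0.721 |
| 17% | 10% vs 6.02% | 0.602 | 0.592 | 8.3% vs 4.32% | 0.688 |

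With f = 10% and the plan's other low-rate pairs, power is 0.631 vs 0.694 at a 5% control rate and 0.715 vs 0.759 at 20%. Restricting helps despite fewer events, because the events removed carry no treatment effect.

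**The case against.** Several counter-arguments have force.

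- **The rule is not explicit.** The plan nowhere says that only the arrest date counts, and in the H1 sentence the time phrase could grammatically attach to the offenses. This stands as a caution. The other descriptions all speak of arrests in a period, so the arrest-date reading is the plain one, and an ambiguity in a primary endpoint is itself worth a sentence.
- **Other covariates help.** The models also adjust for baseline delinquent behavior and for youth- and parent-reported police contacts short of arrest. These may absorb part of the problem, though they do not remove the events. In de-identified data they may be missing.
- **Assignment may not be irrelevant.** A reader might infer that these events cannot respond to assignment at all. The documents do not support that. H1 needs a court-related arrest, and Study Measures notes that cases diverted or handled solely by police are not captured. Whether an arrest or referral follows a recent offense could be settled after randomization. Only the offense itself is beyond the program's reach.
- **The share is of arrests, not youths.** A youth who also has an arrest for a post-enrollment offense is positive under either rule, so fewer youths change status than the shares suggest.
- **Mixed definitions.** A reader might infer that identified and de-identified jurisdictions use two different endpoints. That is largely unsupported: both count by arrest date, and the five H1 categories are broad. An offense-date rule could itself create a mismatch where a data holder cannot apply it.
- **Late change.** The 18-month analyses were already in progress at this revision, which argues against redefining that primary outcome now.

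**Conclusion.** The point holds as a modest loss of sensitivity in a primary endpoint. As plainly read, H1 counts arrests for offenses that predate enrollment, and the field needed to separate them is expected in the records. A reader might infer bias toward one arm; random assignment rules that out in expectation. Nor do the documents show that families seek mentoring after a youth gets into trouble, so a peak in offending before enrollment is only a possibility.

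The size rests on assumed lags and constant offending: about 3-17% of arrests at 18 months and 1-6% at 4 years. The 4-year outcome, which supersedes the earlier one for the multiplicity adjustment, is the less affected. In the 10% vs 5.2% case, the offense-date rule raises power from 0.727 to 0.748 at a 4% share and from 0.667 to 0.721 at a 10% share. Repeat arrests and offending that rises with age would make the gain smaller.

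**What to change.** **4-year outcome.** Before the second records pull, define an H1 event as an arrest within the window, for one of the listed offense types, with an offense date on or after study enrollment. Ask holders of de-identified records to build the outcome indicator by that rule where they can, and report which could not. Present the arrest-date version as a sensitivity analysis.

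**18-month outcome.** Keep the arrest-date definition as primary. Add the offense-date version as a labelled sensitivity analysis where offense dates exist.

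**Baseline covariate.** Leave it as arrests before enrollment. Moving later arrests for earlier offenses into it would put a post-randomization event into a baseline variable.

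**Cost.** One sentence in Primary H1, one in the data request, and one added 18-month sensitivity analysis. The drawbacks are slightly fewer counted events and some jurisdictions that may be unable to apply the rule.

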At the 4-year assessment, the following measures will be added that are relevant to Secondary Hypothesis H3: **Suicidal ideation** (YS; dichotomous measure indicating whether youth reports suicidal ideation during the past 4 years based on response to an item adapted from the *Youth Risk Behavior Survey YRBS*); **Suicide attempt** (YS; dichotomous measure indicating whether youth reports having attempted suicide during the past 4 years based on response to item adapted from the YRBS); **Substance abuse (YS)**: 10 items adapted from the Difficulties subscale of the *Substances and Choices Scale*, Christie et al., 2007) which measures the extent to which substance use has negatively affected the youth’s life (e.g., “My alcohol or drug use has led to arguments with the people I live with (family, roommates or caregivers, etc.”) and asked only of youth who reported using any substance other than tobacco or vaping of tobacco in the previous 6 months; **Sexual intercourse without a condom** (YS: dichotomous measure of condom use during last sexual intercourse, adapted from the YRBS 2021, asked only for those who report ever having had sexual intercourse); **Teen pregnancy** (YS; dichotomous measure from the YRBS 2017 adapted to ask about past 4 years, asked only for those who report having ever had sexual intercourse); **Having a sexually transmitted infection (STI)** (YS: dichotomous measure); **Perpetrating dating violence** (YS; 7-item measure of involvement in perpetrating dating violence in the past four years; four items adapted from Miller et al., 2020 and three items adapted from The National Longitudinal Study of Adolescent to Adult Health (Add Health)), asked only of those who report ever having been in a dating relationship); **Discontinuing education prior to high school diploma** (YS/PS; based on single item asking if youth has graduated from high school with discontinuation indicated by youth or parent endorsement of any of the following options (parent survey wording: No, but my child is working on his/her GED, No, but my child received his/her GED, or My child is no longer attending high school and is not currently working on their GED, and lack of discontinuation indicated by endorsement of either of the following options: No, my child is still attending middle or high school or Yes, my child graduated from high school; conflicting youth and parent responses will be treated as missing); **Meaningful engagement in post-secondary education, training, or employment** (YS/PS; a dichotomous measure based on responses to a single item, asked everyone except those currently attending middle or high school, with meaningful engagement indicated by youth or parent endorsement of any of the following options: Attended a 4-year college or university, Attended a 2-year community college, Participated in a job training or career program (including attending a program or school to get certified or licensed to do a particular type of job), Had a full-time job, Had an internship, Enlisted in the military or “Other” response indicating one of these activities based on coding blind to study condition); **College attendance** (YS/PS; a dichotomous measure based on endorsement, for the same item used for meaningful engagement, of either of the following: Attended a 4-year or 2-year college or university); **Stability of living situation** (YS/PS; a dichotomous measure based on response to a single item asking about the consistency of the youth’s current housing, with unstable housing indicated by response of “Different places from week-to-week or month-to-month (e.g., hotel, motel, “couch surfing” at friends’ or family’s homes)” or “Other” response coded as unstable housing based on coding blind to study condition); **Occupational identity** (YS; five items adapted from the *Social Capital Assessment + Learning for Equity (SCALE) Measures*, Search Institute, 2021, assessing the degree to which the youth has a clear sense of their occupational identity); **Specific job/career goal** (YS: dichotomous measure based on youth’s response to a single item adapted from Resnjanskij et al., 2021, asking whether there is a specific job or career the youth wants when they get older, and for a description of the job/career if applicable, with the latter responses needing to legitimately refer to a job or career based on review blind to study condition and non-qualifying responses treated as missing); **Extra-familial adult with whom youth can discuss their future** (YS; single item adapted from Resnjanskij et al., 2021); **Progress toward education or career goals** (YS; average of responses to 4 questions adapted from the *SCALE measures*, Search Institute, 2021, asked only of youth who report having an education or career goal, about the extent to which they are making progress toward their education or career goals); **Network support for education/career goals** (YS; average of 5 questions adapted from the *SCALE measures*, Search Institute, 2021, asked only of youth who report having an education or career goal); and **Special interest related to future job/career** (YS; dichotomous measure based on

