**Secondary H2:** Program participation will *increase* protective factors for delinquent/criminal behavior (i.e., conventional values, self-esteem, happiness, life satisfaction, coping efficacy, goal setting and pursuit, grit, social skills, self-advocacy, self-control, peer, parent, and significant other perceived social support, school engagement, academic success, involvement in out-of-school activities, spark development, hopeful future expectations, college exploration, career exploration, volunteering, parenting behaviors, and family functioning, again combining across reporter for the measures with both youth and parent data – i.e., self-control and academic success, the measures of each being treated as continuous measures) as assessed 18 months after enrollment and again 4 years after enrollment; and

**Secondary H3:** Program participation will decrease longer-term potential correlates of delinquent/criminal behavior during adolescence (i.e., suicidal ideation and attempts, sexual intercourse without a condom, teen pregnancy, having an STI, substance abuse, perpetrating dating violence, discontinuing education prior to receiving a high school diploma [for those 16 years of age or older], not being engaged in post-secondary education, training, or employment [this outcome will be examined only for those who have discontinued their education, but are not working on a GED, or have received their high school diploma or GED], college attendance, living in unstable housing, lack of occupational identity, no job/career goal, no extra-familial adult with whom the youth can discuss their future, little progress toward education or career goals, lower network support for education/career goals, no special interest related to future job/career. All measures will be dichotomous as defined earlier in this document, with the exception of substance abuse, perpetrating dating violence, occupational identity, progress toward education or career goals, education/career network strength, and lack of an extra-familial adult with whom the youth can discuss their future, which will be treated as continuous) 4 years after enrollment.

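### The d = .17/.18 power statement does not hold for secondary measures collected from only part of the sample at 4 years, and post-secondary engagement is compared in a group formed after randomization

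*Combined protocol and SAP*

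**What the plan says.** All references are to the combined protocol and SAP.

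**Power (Analysis, power paragraph).** With about 1,350 youth, 3:1 allocation and 20% attrition, the plan states power of .80 or more at d = .18 (covariates explaining 15% of variance) or d = .17 (25%). It applies this to all secondary measures that are not dichotomous. It concedes lower power for dichotomous Secondary H3 outcomes that do not apply to everyone, naming post-secondary engagement as its example.

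**Who is asked at 4 years (Study Measures).** Eleven secondary measures carry an explicit filter:
- School misbehavior and truancy: youth not in college.
- School engagement: youth still in school or college.
- Parenting behaviors and family relationships: parents whose child lived with them for some of the past year.
- Substance abuse: "asked only of youth who reported using any substance other than tobacco or vaping of tobacco in the previous 6 months".
- Intercourse without a condom: "asked only for those who report ever having had sexual intercourse".
- Teen pregnancy: "asked only for those who report having ever had sexual intercourse".
- Dating violence: "asked only of those who report ever having been in a dating relationship".
- Goal progress and network support: youth with an education or career goal.

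No value is stated for youth outside these filters. By contrast, the job-related special-interest item has a stated code for youth who are not asked it.

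**Engagement (Analysis, Secondary H3).** The item is "asked everyone except those currently attending middle or high school". The analysis is narrower: "this outcome will be examined only for those who have discontinued their education, but are not working on a GED", or who hold a diploma or GED. The same hypothesis lists "discontinuing education prior to receiving a high school diploma" among the things the program should reduce.

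**Missing data (Analysis).** Multiple imputation is planned under missing at random. Items skipped by design are not mentioned.

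**The concern.** There are three linked issues.

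- **Power.** A reader would take .80 power at d of about .18 as applying to each continuous secondary outcome. If a measure exists for only part of the sample, a null result on it would be read as stronger evidence than it is.
- **Engagement.** School or GED status at 4 years is reached after assignment and may respond to it. Comparing arms within that status compares groups that randomization did not form.
- **Skipped items.** Two analysts could both follow the plan and differ, one imputing a value for a youth to whom an item does not apply and the other dropping that youth.

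**Working it through.** **1. Reproduce the stated figure.** Inputs from the power paragraph and the allocation text: 1,350 × .80 = 1,080, split 3:1 into 810 treated and 270 control. No alpha is stated for secondary tests; two-sided .05 is assumed.

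Detectable d = (1.960 + 0.842) × √(1/270 + 1/810) × √(1 − R²)

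- R² = .15: 2.802 × 0.0703 × 0.922 = .182
- R² = .25: 2.802 × 0.0703 × 0.866 = .170

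These match .18 and .17. A one-sided test gives .161 and .151, which do not. The stated figures therefore use every post-attrition youth, with nothing lost to filters.

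**2. Apply a filter.** If a share f answers in each arm, detectable d is divided by √f. The plan gives no f, so a range is shown.

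| f (assumed) | n | Detectable d, R² .15 / .25 | Power at d = .18 (R² .15) / d = .17 (R² .25) |
|---|---|---|---|
| 1.00 | 1,080 | .182 / .170 | .79 / .80 |
| .90 | 972 | .191 / .180 | .75 / .76 |
| .80 | 864 | .203 / .191 | .70 / .71 |
| .70 | 756 | .217 / .204 | .64 / .65 |
| .50 | 540 | .257 / .241 | .50 / .51 |
| .30 | 324 | .331 / .311 | .33 / .33 |

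**3. Which measures this reaches.** School engagement, parenting behaviors, family relationships, goal progress and network support are continuous, filtered, and have no logical value for those not asked. Dating violence and substance abuse join them only if analysed among those asked. School misbehavior and truancy are filtered too, but they are dichotomous Secondary H1 outcomes, so neither the d statement nor the H3 warning describes them.

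**4. Engagement: who leaves the comparison.** A youth who graduates instead of leaving school is inside the analysed group either way. A would-be leaver who is still in high school, or working on a GED, at 4 years is outside it. The Overview says that "by this latter time point roughly two-thirds of the sample will be at least 16 years old". If younger youth are all still in school, at most about 1,080 × 2/3 = 720 enter.

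**5. Engagement: possible size (all rates assumed).** Let 40 of every 100 youth enter without mentoring. Finishers are 20% not engaged and leavers 60%. Mentoring keeps 25% or 50% of leavers in high school, where all of them still are at 4 years, and changes nothing for anyone who remains in the group.

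| Finished / left | Not engaged, no mentoring | 25% retained | 50% retained |
|---|---|---|---|
| 36 / 4 | 24.0% | 23.1% | 22.1% |
| 34 / 6 | 26.0% | 24.7% | 23.2% |
| 32 / 8 | 28.0% | 26.3% | 24.4% |

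Example, 34/6 with 50% retained: (6.8 + 3.6)/40 = 26.0% becomes (6.8 + 1.8)/37 = 23.2%. Across the table the apparent improvement runs from 0.9 to 3.6 points. With 40% entering, n = 432 (108 control, 324 treated), and the detectable difference from 26% is 12.1 points (pooled formula) or 12.3 (arcsine).

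**The case against.** **On power.** The plan says its estimates depend partly on matters that can be settled only at analysis. It also recognises that some outcomes do not apply to everyone. Routing a question need not fix the analysis population: the 4-year substance-use items go only to users, yet the outcome is a 0/1 variable for youth generally. If dating violence and substance abuse were coded for everyone, n would return to 1,080 and .18/.17 would apply. That point stands for those two. It does not rescue the other five, and the warning as worded covers only dichotomous H3 outcomes. Some filters may also pass nearly everyone; co-residence with a parent is a plausible case. The 90% and 80% rows are in the table for that reason.

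**On engagement.** The restriction is largely definitional, since post-secondary activity has little meaning for a youth still in school. Diploma and GED holders are inside the group, so a reader who infers that an effect on leaving school automatically changes membership goes too far. Only still being in school, or working on a GED, does that. Assuming that every retained leaver is still in high school makes 0.9 to 3.6 points an upper-end illustration for the rates chosen. This all stands, and it limits the size of the issue without making the comparison a randomized one.

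**On skipped items.** A reader might infer that values will be imputed for youth who never dated or never had intercourse. The plan does not say so; it is silent. A reader might also infer that all eleven filtered measures will be analysed only among those asked. That is likely but not stated.

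**Conclusion.** The point holds, and it should be fixed.

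- **Power.** The statement is wrong as written for five continuous secondary measures at 4 years, and for two more if they are analysed among those asked. The loss ranges from slight (power .75 if 90% answer) to severe (.33 if 30% answer). The documents do not say where each measure falls. The warning also omits school misbehavior and truancy at 4 years.
- **Engagement.** The contrast is conditional on a status reached after randomization. Under assumed rates the distortion is well below what the trial could detect, so it mainly affects how a result may be described. The documents do not support reading this as a large bias.
- **Skipped items.** This is missing detail. None of the eight listed sensitivity analyses addresses selection into a filter.

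The primary outcomes and their Benjamini-Hochberg family are untouched.

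**What to change.** Before the 4-year data are analysed by arm:

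1. Restate the power paragraph so that d = .18/.17 applies only to measures analysed in the full sample. Give detectable d by answering share for filtered continuous measures. Extend the reduced-power warning to school misbehavior and truancy at 4 years.
2. Define the engagement population by a baseline variable such as age, counting youth still in school as not having the adverse outcome. Alternatively, keep the restriction and label the contrast conditional and descriptive. State how youth working on a GED are handled, both for engagement and for college attendance, which uses the same item and has no stated population.
3. State that values skipped by design are not imputed as missing at random, and report the share passing each filter by arm.
4. Where the value is logically known (never had intercourse, never dated), add a whole-sample coded analysis beside the within-filter result. Replacing the within-filter result is not required, because the two answer different questions. A substance-abuse recode should not be required unless non-use over the same window is recorded at 4 years.

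The cost is SAP wording, one further analysis for each outcome recoded under item 4, and a less favourable stated power. The whole-sample results will partly reflect abstinence.
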